4.3 Local and Central POC Test Result versus GenScript cPass Assay

The GenScript assay will also be conducted on the specimens at the central laboratory. The locally and centrally determined POC results will be compared to the GenScript result using McNemar's chi-square test and will be supplemented by 95% CIs for the difference in the probability of testing positive. Investigation of site effects and test performance in subgroups will be pursued as described in Section 4.2.

4.4 Association of POC Test Results with TICO Outcomes: A Nested Case-Control Study of Completed TICO Trials

TICO specimens selected for the case-control study will be shipped from the repository at Advanced Biomedical Labs LLC to the central laboratory for analysis. The Fine-Grey approach to competing risk regression will be used to test for an association between the POC test result and time to sustained recovery while controlling for the parent sub-study effect. A significance level of 0.05 will be used to test the null hypothesis that the regression coefficient associated with the presence of antibodies at baseline is zero. The association between baseline POC test results and time to death will be investigated using Cox models stratified by parent sub-study. The association between baseline POC test results and the primary safety composite at days 5, 28 and 90 will be investigated using logistic regression models that control for parent sub-study.

Finally, data will be pooled from the field test and the stored specimens for all qualitative assays conducted to test for differences. This would include the local POC, central POC, and GenScript results from the field test, the GenScript result for the stored specimens and the POC results for the stored specimens. This analysis will use generalized estimating equations for binary outcomes with effects for the type of assay (3 values), if the assay was conducted locally or centrally, and in which protocol/sub-study the participant enrolled. The association due to the specimen coming from the same person will be accounted for by including this information as a clustering effect in the model. Tests for differences in the assays will be based on the Wald test for the regression coefficients for the assays. No multiplicity adjustment will be made for these tests.

Associations between qualitative antibody and continuous antigen assays will be examined using 2 by 2 tables by dichotomizing the antigen assay results at the median level for a given trial, and Fisher's exact test will be used to test for an association. Logistic regression models will be used to compute adjusted odds ratios where adjustment will be made for parent study and site (where sites may be grouped as described above).

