3.2 Study Objectives

3.2.1 Field test

The overall objective of the field test is to determine if a POC test can be used to identify individuals who lack endogenous antibodies. The **primary objective** is to test for an association between the outcome of the locally obtained POC test and the centrally obtained result from the GenScript assay on a blood sample obtained at the same time as the sample for the POC test. There are also a number of secondary objectives that will investigate the feasibility of this approach, and others that will help interpret the outcome of the primary objective. These are as follows:

1. Determine the frequency with which the POC test fails to give an unambiguous result.
2. Determine the time required to obtain a POC result.
3. Determine the magnitude of the association between the locally obtained POC test result by the 20-30 sites and the same POC assay on the same specimens determined centrally after processing, freezing, storing, and shipping.
4. Determine the magnitude of the association between the POC test result and the GenScript assay on the same specimens both determined centrally.

Secondary objective 3 will provide information on the impact of processing (centrifugation for plasma), freezing, storing, and shipping on the test results using the same assay while secondary objective 4 will provide a head-to-head comparison of the assays using the same specimen subjected to the same handling procedures. Specimen handling and the specific assay used both likely contribute to differences we may observe between the local POC test and the results from the GenScript assay.

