3.2.2 Central laboratory

The overall objective of central testing of stored specimens is to understand the impact of baseline serology, as assessed by the POC tests, on outcomes of relevance for the TICO trial. The **primary objective** is to test for an association between the POC test result on stored baseline specimens and the primary efficacy outcome in TICO on a subset of specimens from TICO participants for whom the GenScript assay has result has already been determined. Secondary objectives are as follows:

1. Test for an association between each POC test result on stored baseline specimens and efficacy/safety outcomes in TICO in a case-control design.
2. Compare the POC test results to the GenScript results and other antibody test results such as those from Bio-Rad and Quanterix that have already been obtained for these stored specimens.
3. Select a threshold for the quantitative LumiraDX result to optimize the association between the dichotomized assay result and safety and efficacy outcomes using the stored specimens.
4. Compare the 2 POC platforms to each other and the GenScript result using locally (at each site) and centrally determined POC results.
5. Examine associations between these antibody assays and antigen assays which have already been obtained for the stored specimens.
6. Determine the effect of vaccination and other participant characteristics on the antibody test results.

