3.3 Sample Size and Statistical Considerations

3.3.1 Local versus central POC test result

The power for comparisons of results from paired qualitative tests on specimens was assessed using Schlesselman's formula for the power of McNemar's chi-square test¹⁰. This requires specification of the odds ratio and the probability of 1 test being positive when the other is negative (denoted p_{01} in the table). Table 1 shows the power as it depends on these 2 parameters with a sample size of 375. By taking the odds ratio to be greater than 1 we are assuming that p_{01} is the smaller of the 2 probabilities of 1 test being positive while the other is negative. For example, $p_{01}=0.01$ and an odds ratio of 2.2 implies that the 2 probabilities that one test is positive while the other is negative are 0.01 and 0.022, and the probability that the 2 tests agree is 96.8%. As can be seen in Table 5, with a sample size of 375 the power of the test is low in this scenario (0.24), but this is fairly strong agreement across the assays. As can be seen from the same table, the test will have over 80% power if $p_{01}=0.03$ and the odds ratio is at least 2.6. This corresponds to the discordance probabilities of 0.03 and 0.078 and the corresponding probability that the 2 tests agree is 89.2%. With this configuration of probabilities for test agreement the standard error for the difference in the probability that the 2 tests are positive is 0.023. There is currently no data available for this comparison.

| Odds ratio | $p_{01}=0.01$ | $p_{01}=0.03$ | $p_{01}=0.05$ |
|------------|---------------|---------------|---------------|
| 2.0 | 0.19 | 0.49 | 0.72 |
| 2.1 | 0.21 | 0.56 | 0.79 |
| 2.2 | 0.24 | 0.62 | 0.85 |
| 2.3 | 0.27 | 0.68 | 0.89 |
| 2.4 | 0.30 | 0.74 | 0.93 |
| 2.5 | 0.33 | 0.79 | 0.95 |
| 2.6 | 0.36 | 0.83 | 0.97 |

Table 5: The power of McNemar's chi-square test for testing the agreement of 2 assays as it depends on the odds ratio and the smaller of the 2 probabilities for test discordance. This assumes the sample size is 375.

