4.2 Local versus Central POC Test Result Comparison

The primary analysis will test if the odds ratio for the association is 1 using McNemar's chi-square test with a significance level of 0.05. Samples for which either test result is missing will be excluded from this analysis. This test will be supplemented by a 95% CI for the difference in the probability of testing positive. Site level effects will be estimated by using generalized estimating equations for Bernoulli outcomes using a logistic link with pairs of results modelled as

being correlated (the test outcome is the binary outcome). This model will include fixed effects for the test type (i.e., local or central) and site. Sites may be grouped based on geography or ICC membership to improve the precision of site level estimates and the interaction between site and test type will be investigated. Subgroups based on age, existence of an immunocompromising condition and vaccination status will be investigated (provided enough individuals with an immunocompromising condition enroll). These subgroup analyses will test for an interaction between group membership and test type. This analysis will be used for both POC tests, and there will not be an adjustment for the conduct of the 2 sets of analyses.

In addition to the primary analysis, associations between test results and participant characteristics will be investigated. These characteristics include age, sex, existence of an immunocompromising condition and vaccination status.

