4.5 Analysis of the Quantitative Results from the LumiraDX Assay

All comparisons that were conducted using the qualitative result from the LumiraDX assay will be repeated using the quantitative result using the appropriate modification of the analysis to accommodate a continuous variable. Comparisons to the RightSign and qualitative GenScript results will use the Wilcoxon rank sum test with the 2 groups being determined by the outcomes of the RightSign or GenScript test (i.e., the ranks of the LumiraDX results for positive and negative results for the other assays will be compared). Adjusted analyses will be pursued using linear regression after transformation (e.g., logarithmic), if appropriate. Comparisons of the locally and centrally conducted LumiraDX assay will be conducted using linear regression with adjustments made by the inclusion of relevant covariates. The quantitative result will also be used in the competing risk regression models as a continuous covariate and as a set of indicator variables that represent the quartiles of the distribution of this assay (to avoid the linearity assumption).

Other approaches to dichotomizing the quantitative LumiraDX results will be investigated and assessed. Potential values to use for dichotomizing the results will be based on deciles of the distribution and for each potential threshold the sub-hazard ratio for the impact of baseline serostatus on time to sustained recovery will be computed. An alternative cut-off may be selected if there are substantial differences in the hazard ratios.

5 Protection of Human Subjects and Other Ethical Considerations

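### The pooled GEE in Section 4.4 gives both POC platforms one local/central effect, so its LumiraDX v RightSign test can mislead if handling affects them differently

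*Combined protocol and SAP*

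**What the plan says.** The last analysis in Section 4.4 pools the local POC, central POC and GenScript results from the field test with the central POC and GenScript results from the stored TICO specimens. The model is a logistic-type GEE, clustered by person, whose listed terms are: "effects for the type of assay (3 values), if the assay was conducted locally or centrally, and in which protocol/sub-study the participant enrolled". Inference is on the assay terms: "Tests for differences in the assays will be based on the Wald test for the regression coefficients for the assays". No assay-by-location interaction is listed. Section 4.2, by contrast, does name interactions for its own model: "the interaction between site and test type will be investigated".

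The comparison has a stated purpose. Secondary objective 4 in Section 3.2.2 is: "Compare the 2 POC platforms to each other and the GenScript result using locally (at each site) and centrally determined POC results".

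On handling, Section 3.2.1 says: "Specimen handling and the specific assay used both likely contribute to differences we may observe". Section 3.3.1 says of local v central results: "There is currently no data available for this comparison".

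**The concern.** Five assay-by-location combinations exist: LumiraDX local and central, RightSign local and central, and GenScript central only. Three assay levels plus one location term cannot describe five free cells. The model closes the gap by making the local/central shift the same for both POC platforms on the logit scale. Nothing in the documents supports that equality. Local testing uses fingerstick whole blood, and central testing uses plasma that has been spun, frozen and shipped. One platform reads fluorescence on an instrument and the other is a lateral-flow strip.

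If the shifts differ, part of the handling effect enters the assay coefficients that are tested. The platform comparison is the most exposed, because no other named analysis tests qualitative LumiraDX against qualitative RightSign. Section 4.2 compares local with central within a platform. Section 4.3 compares POC with GenScript. Section 4.5 uses the quantitative LumiraDX result ("Comparisons to the RightSign and qualitative GenScript results will use the Wilcoxon rank sum test"). A single blended coefficient could report a platform difference that does not exist under central handling while understating the one at the bedside, which is the setting the field test is about.

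**Working it through.** **A figure to anchor on.** The plan gives no power or effect size for the pooled GEE. The nearest figure is the McNemar power in Table 5 for discordance probabilities 0.03 and 0.078:

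- discordant pairs m = 375 × (0.03 + 0.078) = 40.5, and P = 0.078/0.108 = 0.722
- z = (0.222 × √40.5 − 1.96/2) / √(0.722 × 0.278) = (1.414 − 0.98)/0.448 = 0.97
- power = 0.83, as stated

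**Cell counts.** There are 375 field participants with five results each and 145 stored specimens with three central results each, and both platforms are run on all specimens. Each POC platform therefore has 375 local and 375 + 145 = 520 central results, 895 in all.

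**What the coefficients estimate.** Let D_loc and D_cen be the true LumiraDX − RightSign differences locally and centrally. H = D_loc − D_cen is then the between-platform difference in handling effect. The two platforms occupy the same cells, so to a close approximation:

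- LumiraDX v RightSign = (375 × D_loc + 520 × D_cen)/895 = 0.42 D_loc + 0.58 D_cen = D_cen + 0.42 H
- The shared location effect is the average of the two platforms' handling effects, so the error of 0.42 H splits evenly. Each POC v GenScript coefficient is off by about 0.21 H, in opposite directions for the two platforms.

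**Illustration.** Assume that only local LumiraDX shifts, by 4.8 points (the size of 0.078 − 0.03 in Section 3.3.1). That only one platform shifts is an assumption. The truth is D_loc = 4.8 and D_cen = 0. The model gives 0.42 × 4.8 = 2.0 points for LumiraDX v RightSign and an error of 0.21 × 4.8 = 1.0 point for each POC v GenScript contrast.

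**Simulation of that case.** There were 4000 runs with no missing results. Base positivity was 46% (Section 2.2). A latent-normal correlation was set to give 10.8% discordance (0.03 + 0.078) for the shifted pair. The fit was a logistic GEE with independence working correlation and robust Wald tests at 0.05; Section 4.4 states no level for these tests.

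Model as listed:
- LumiraDX v RightSign rejects 47%. Its 95% CI covers the true local value 28% of the time and the true central value 53%. The log OR is 0.083 against 0.192 locally, a ratio of 0.43, which agrees with the algebra.
- RightSign v GenScript, equal in every cell, rejects 11.8%.
- Central LumiraDX v GenScript, also equal, rejects 12.6%.

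Five-level assay-location factor:
- central LumiraDX v RightSign rejects 5.4% and RightSign v GenScript 4.6%
- local LumiraDX v RightSign has 83% power
- CI coverage is 95%

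**Sensitivity (model as listed unless stated).**
- Discordance of 14% and 20%: LumiraDX v RightSign rejects 38% and 27%; RightSign v GenScript 10.1% and 9.4%.
- A shift of 2 points: 12.8% for LumiraDX v RightSign and about 6% for the GenScript contrasts. A shift of 1.2 points: 8.2% and 5–6%.
- Central LumiraDX shifts by −4.8 points instead: its true difference from GenScript is understated by 21% (log OR −0.155 v −0.197), with power 82% v 93% under the five-level factor. RightSign v GenScript rejects 12.8%.
- Equal shifts on both platforms: 4.1–4.7%. No shift: 4.5–5.7%.
- Exchangeable working correlation (3000 runs, 4.8-point local shift): 47% and 11.6%.

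**The error can also hide differences.** Take LumiraDX at 46% local and 52% central, and RightSign at 52% local and 47.7% central. The true RightSign/LumiraDX odds ratios are 1.27 locally and 0.84 centrally, yet the pooled odds ratio is 1.00. A separate simulation (400 runs, within-person latent correlation 0.9) gave 5% rejection.

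**The case against.** - **Section 4.4 does not exclude an interaction.** True; the reading rests on the terms it lists. But those terms and the assay coefficients are all an analyst has to follow. Adding a term after seeing the Section 4.2 results would be post hoc.
- **Differential handling is assumed.** Both platforms face the same change from fingerstick blood to frozen plasma, so partly shared shifts are plausible. With same-direction shifts of 4.8 and 2.4 points, LumiraDX v RightSign rejects 15% and the GenScript contrasts 7–8%. If discordance stays at 10.8% within a platform but is set at 15%, 20% or 25% between assays, LumiraDX v RightSign rejects 28%, 20% or 17%, and the GenScript contrasts 7–10%. This stands as a limit on size: 47% is near the top of a wide range.
- **47% is not a false-positive rate.** Correct. The platforms do differ locally in that case, so for LumiraDX v RightSign the fault is an undeclared blend whose weights come from recruitment numbers. Only the GenScript contrasts show inflated size proper.
- **Other analyses cover much of this.** Section 4.3 says: "The locally and centrally determined POC results will be compared to the GenScript result using" McNemar's test, with CIs, and Section 4.2 tests each platform's local v central shift. Neither uses the shared effect, and Section 4.2 would often reveal a shift (power 0.83 in the case above). That limits the exposure on GenScript. It supplies no test of LumiraDX v RightSign and does not correct the pooled one.
- **The analysis is secondary.** True. Neither primary objective nor any data collection depends on it.

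**Conclusion.** The concern holds in its conditional form. As listed, the pooled model is right only if handling moves both platforms equally on the logit scale, and the documents offer no evidence for that. The 42/58 blend follows from the planned numbers alone. How often the tests mislead depends on assumed shifts, discordance and base positivity: little at 1–2 points, substantial near 5 points on one platform. The damage is confined to the pooled Wald tests, chiefly the platform comparison under secondary objective 4 of Section 3.2.2. The change should be made because the better specification costs almost nothing.

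**What to change.** Before the analysis, replace the assay and local/central effects in Section 4.4 with one five-level factor: LumiraDX local, LumiraDX central, RightSign local, RightSign central, GenScript central. Giving each POC platform its own local/central term is equivalent. A full 3 × 2 interaction cannot be fitted, because GenScript is never run locally.

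Base the Wald tests on named contrasts:
- LumiraDX v RightSign, local v local and central v central
- each central POC result v GenScript
- each local POC result v GenScript
- local v central within each platform

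If one overall platform comparison is wanted, define it as the average of the local and central contrasts and report both parts beside it.

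The cost is one parameter (four degrees of freedom in place of 2 + 1 = 3), two sentences of text and no new data. If handling effects are in fact equal, the standard error of the log OR for POC v GenScript rises from 0.053 to 0.056. The separate LumiraDX v RightSign contrasts have standard errors of 0.056 (central) and 0.066 (local), against 0.043 for the blended coefficient. The averaged contrast keeps 0.043.

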2.2 Background

TICO is a platform trial designed to efficiently identify treatments for adults who have been hospitalized with COVID-19. A manuscript providing details on the protocol has been published⁷ so here a brief description of the trial is provided. As a platform trial, multiple agents can be investigated simultaneously which allows for efficiencies due to a shared placebo group. Each investigational agent is studied in a randomized placebo-controlled trial with an early futility assessment based on two 7-category ordinal outcomes assessed at day 5 of follow-up to assess efficacy and a composite of grade 3 and 4 adverse events (AEs), serious adverse events (SAEs), clinical organ failure or serious infection or death through day 5 to assess safety. The primary efficacy outcome is time to sustained recovery, which is the first time after

randomization at which someone returns to their pre-hospitalization residence and stays there for 14 days prior to day 90. All-cause mortality through 90 days of follow-up is an important secondary outcome.

Thus far, 6 agents have entered the platform trial with the first 4 being nMabs or combinations of nMabs. These agents are as follows:

1. Bamlanivimab.
2. Sotrovimab (also referred to as VIR-7831).
3. BRII-196/198.
4. AZD7442.
5. MP0420.
6. PF-07304814.

The study has been completed and papers have been written describing the outcomes for the first 3 compounds, while the results for the remainder are still blinded. These 3 trials were stopped for futility at the time of the early futility assessment. Baseline antibody results are available for the first 3 compounds using the GenScript assay.

Analyses of the qualitative GenScript results from participants in the placebo arm of the first 3 trials (n=320) found that being seropositive was associated with superior efficacy and safety outcomes. Competing risk regression was used to test for an association between the baseline qualitative result from the GenScript assay and time to sustained recovery. The result was statistically significant with a sub-hazard ratio of 1.45 and a 95% confidence interval (CI) of (1.17, 1.81). The estimated hazard ratio for death (positive/negative) was 0.17 with a 95% CI of (0.05, 0.57), hence also statistically significant⁶.

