While the semi-quantitative GenScript results do not have any authorization for use in patient management, there is evidence that the use of different thresholds for dichotomizing this semi-quantitative result leads to different estimates of the magnitude of the association between the antibody test and time to sustained recovery. By using a lower threshold for antibody levels and thereby reducing the specificity and increasing the sensitivity for being seropositive, one detects a stronger association. The threshold used for the qualitative result finds that 46% of the 320 participants in the placebo arm are seropositive. If the threshold is lowered so that 58% of the participants are seropositive, we find that the sub-hazard ratio increases from 1.45 to over 1.6.

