A nested case-control study will also be conducted to allow for testing of the association between antibody levels at baseline, as assessed by the POC tests and safety and efficacy outcomes among participants randomized to the placebo group in the bamlanivimab, sotrovimab, and BRII-196/198 trials of TICO. The case definition is death or time to sustained recovery that exceeds 28 days. To maximize the difference between cases and controls, controls are defined as those with a time to sustained recovery of no more than 16 days. With these definitions there are 68 cases and 77 controls for a total sample size of 145. Among these participants, 104 experienced a sustained recovery and 20 died.

Conduct of this nested case-control study will require use of the POC assay on stored specimens. One cannot conduct such tests in a batched fashion which makes this analysis time consuming. This testing will be facilitated by procuring multiple POC platforms at a central location. The use of multiple platforms will allow for multiple tests to be conducted in parallel which is more efficient since each specimen must be run one at a time, and each takes 10-20 minutes.

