3.3.2 Local and central POC test result versus GenScript cPass assay result

Sample size considerations for these comparisons are similar to those from the previous section, but we do have data from 302 participants on the relationship between the central POC test using the RightSign platform and the GenScript assay using stored specimens for both assays. The association depends on which isotype is measured with the RightSign assay: there is evidence that the odds ratio is different from 1 for IgM (odds ratio 7.5, $p<0.001$) but not for IgG (odds ratio 1.1, $p=0.82$). These preliminary data indicate that 375 samples obtained as part of the field test will provide more than adequate power for detecting a difference for the GenScript assay and RightSign IgM assay and very low power for detecting a difference between the GenScript assay and the RightSign IgG assay due to the high degree of association between the latter pair of assays.

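### The antibody–antigen test splits a continuous antigen result at the trial median; this is valid, but a trial-stratified rank test would usually have more power

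*Combined protocol and SAP*

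**What the plan says.** Section 3.2.2 (central laboratory, secondary objective 5) sets the aim: "Examine associations between these antibody assays and antigen assays which have already been obtained for the stored specimens".

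The analysis is in the last paragraph of section 4.4. It describes the antibody results as qualitative and the antigen results as continuous, then builds 2 by 2 tables "by dichotomizing the antigen assay results at the median level for a given trial" and tests them with Fisher's exact test. Logistic regression supplies odds ratios adjusted for parent study and site. The paragraph does not say whether antigen is continuous or split in those models, and gives neither a reason for the split nor a power figure.

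Section 4.5 adds, for one platform, "All comparisons that were conducted using the qualitative result from the LumiraDX assay will be repeated using the quantitative result". For a continuous assay against a qualitative one, that section chooses a rank test: "Comparisons to the RightSign and qualitative GenScript results will use the Wilcoxon rank sum test".

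On the number of stored specimens with point-of-care results, section 3.1 says: "With these definitions there are 68 cases and 77 controls for a total sample size of 145".

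**The concern.** A median split treats a value just above the median and one far above it as the same. For most continuous distributions this discards information that a rank test keeps. At 145 specimens a moderate antibody–antigen association could then be missed by the named test although the same data would show it under a rank test.

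Two parts of the plan might recover the loss, but neither clearly does. The adjusted logistic models would help only if antigen enters them as continuous, which is not stated. Section 4.5 makes the LumiraDX antibody result continuous. It does not say that antigen stays continuous, and it does not cover RightSign or the qualitative GenScript result.

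What is at stake is power in one secondary objective, not bias, and neither primary objective is involved.

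**Working it through.** **Stated figure.** The plan gives no power or effect size for this analysis, so there is none to reproduce.

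**Inputs from the documents.**
- n = 145, from 3 parent trials (section 3.1).
- 46% seropositive (section 2.2: "The threshold used for the qualitative result finds that 46% of the 320 participants in the placebo arm are seropositive"). This is a GenScript figure from unselected placebo participants, used here as a stand-in.

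**Assumptions.**
- Two-sided 0.05.
- Antigen = noise with SD 1, minus a shift for seropositives.
- Planned test: each value classed as above or below the median of its own trial's analysed specimens, tables pooled, Fisher's exact test.
- Alternative: van Elteren test with weights 1/(n_t + 1), where n_t is the number of specimens in trial t.
- 6,000 simulated data sets per power setting, 10,000 for null and step settings; Monte Carlo SE at most 0.007.

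**Step 1, validity.** With no association, rejection rates were 0.047 (Fisher) and 0.052 (van Elteren). With assumed trial differences (antigen shifts 0, 0.5 and 1 SD; seropositivity 30%, 46% and 60%) they were 0.041 and 0.052. The planned test is valid and slightly conservative.

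**Step 2, theory.** The asymptotic efficiency of the median test relative to Wilcoxon is f(m)² / [3(∫f²)²], where f is the density and m its median.
- Normal: (2/π)/(3/π) = 2/3.
- Logistic: (1/16)/(3/36) = 3/4.
- Laplace: (1/4)/(3/16) = 4/3.

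For normal data the planned test on 145 specimens should act like the rank test on 145 × 2/3 ≈ 97.

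**Step 3, hand check at 0.5 SD, normal, ignoring trial.**
- Median split: the mixture median is −0.23, so the proportions above it are 0.591 (seronegative, n = 78.3) and 0.393 (seropositive, n = 66.7). The null SE is √[0.25(1/66.7 + 1/78.3)] = 0.0833 and the alternative SE is 0.0816. Then (0.197 − 1.96 × 0.0833)/0.0816 ≈ 0.42, which is power 0.66 before Fisher's conservatism.
- Rank test: the probability that a seronegative value exceeds a seropositive one is Φ(0.5/√2) = 0.638. Then √(12 × 145 × 0.46 × 0.54) × 0.138 − 1.96 = 20.79 × 0.138 − 1.96 ≈ 0.91, which is power 0.82.

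**Step 4, simulated power at n = 145.**

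| Setting | Planned Fisher | Stratified rank |
|---|---|---|
| Normal, 0.3 SD | 0.27 | 0.40 |
| Normal, 0.4 SD | 0.44 | 0.62 |
| Normal, 0.5 SD | 0.63 | 0.82 |
| Normal, 0.8 SD | 0.96 | 0.99 |
| Normal, 0.5 SD, trial effects as in step 1 | 0.57 | 0.79 |
| Normal, 0.5 SD, 30% seropositive | 0.53 | 0.75 |
| Normal, 0.5 SD, 60% seropositive | 0.62 | 0.82 |
| Normal, 0.5 SD, 40% of values at an assay floor | 0.63 | 0.77 |
| Normal, 0.5 SD, 60% of values at an assay floor | 0.62 | 0.70 |
| Logistic, 0.5 SD | 0.74 | 0.86 |
| Uniform, 0.5 SD | 0.39 | 0.79 |
| Laplace, 0.5 SD | 0.93 | 0.93 |
| Step at median, 20 points | 0.55 | 0.54 |
| Step at median, 25 points | 0.76 | 0.73 |
| Step at median, 30 points | 0.89 | 0.88 |

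In the step rows, seropositivity differs by that many percentage points between values above and below the median. Repeat simulations of the normal shifts agreed to within about 2 points.

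**Step 5, equivalent sample size at a normal 0.5 SD.** The rank test has power 0.61 at n = 95 and 0.65 at n = 100, which brackets the planned test's 0.63 at n = 145. In the other direction, Fisher needs about 220 to 235 specimens to match the rank test on 145; theory gives 145 × 3/2 = 217.5.

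**Step 6, larger sets.** Section 2.2 reports "Analyses of the qualitative GenScript results from participants in the placebo arm of the first 3 trials (n=320") and section 3.3.2 says "we do have data from 302 participants on the relationship between the central POC test using the RightSign platform and the GenScript assay". Whether antigen results exist for all of these is not stated. If they do, the normal-shift figures are as follows:

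| n | 0.3 SD, Fisher v rank | 0.5 SD, Fisher v rank |
|---|---|---|
| 302 | 0.52 v 0.70 | 0.92 v 0.99 |
| 320 | 0.54 v 0.73 | 0.94 v 0.99 |

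**The case against.** The strongest reply is that nothing here is an error. The planned test is valid, and the objective is exploratory in tone, is fifth of six, and carries no stated power. The median split also puts the test and the odds ratio on one scale in a protocol concerned with positive and negative calls; under the alternative, the rank p-value and the logistic odds ratio could disagree. Section 4.5 may cover part of the LumiraDX comparison, and the logistic models may already use continuous antigen. The size of the loss rests on assumed distributions and on a seropositive share from a different set of participants.

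Most of this stands as a limit on weight, and it is why the point is minor. It does not remove the point. The possible disagreement between p-value and estimate is a real cost, reduced by stating how antigen enters the logistic model. Values at an assay floor narrow the gap but left 8 points at 60% (0.62 v 0.70). The possible recoveries are unwritten for antigen, and RightSign and the qualitative GenScript result stay uncovered.

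The wording could also mean the median of the full trial, or a separate table for each trial. The calculations use the median of the analysed specimens and one pooled table; the other readings were not simulated.

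**Conclusion.** The point holds as a low-priority improvement. The planned test controls type I error but usually has less power than a trial-stratified rank test on the same values. The loss at 145 specimens is about 13 to 19 points for normal shifts of 0.3 to 0.5 SD, and only 3 points at 0.8 SD. It is nil for a Laplace distribution, and the planned test leads by 1 to 3 points if the effect is a step at the median. The direction is robust across most settings tried. The size is illustrative, because the antigen distribution, the effect size, the split across trials and the seropositive share among the 145 are all assumed. If the logistic models use continuous antigen, only the unadjusted test is affected.

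**What to change.** In the last paragraph of section 4.4:

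1. Make the main unadjusted test a Wilcoxon rank sum test of antigen by serostatus, stratified by parent trial (van Elteren). This extends the approach of section 4.5, and the stratification keeps the protection that trial-specific medians give.
2. Keep the median-split 2 by 2 table as a descriptive display.
3. Keep the adjusted logistic models as the source of the odds ratio, and state in one clause whether antigen enters as continuous or split. This clause is worth adding even if Fisher's test is kept.
4. State whether the median used for the display is that of the full trial or of the specimens analysed, and whether the tables are pooled.

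The cost is a change of wording, with no new data or assays. The rank test gives no odds ratio of its own, so its p-value and the logistic estimate may occasionally differ, and about 1 to 3 points of power may be lost in the unfavourable cases above.
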